### 5.3. OTHER ENDPOINTS

Not applicable

### 5.4. COVARIATES

Variable	Role	Operational definition
Previous stroke		
Previous incidence of stroke	Patient characteristic:	
Previous incidence of TIA	Patient characteristic:	Defined elsewhere using ICD-10 codes

PFIZER CONFIDENTIAL

Types of previous stroke	Patient characteristic:	cardioembolic stroke or cerebral infarction
Treatment status	Patient characteristic:	Inpatients or outpatients
Hospitalization days	Patient characteristic:	0 or days in hospital
NVAF diagnosis and treatment		
Year	Patient characteristic	Year first diagnosed with NVAF
Anticoagulant	Patient characteristic	Warfarin or apixaban
Patients		
age	Patient characteristics on index date	Years
Age category	Patient characteristics on index date	
age $\leq 65$		
age $65 < , \leq 75$		
age $75 <$		
Gender category	Patient characteristics on index date	Male or female
Body weight	Baseline characteristic	Kg (if available)
Height	Baseline characteristic	cm (if available)
BMI	Baseline characteristic	Calculated from body weight and height using a formula of (weight [kg]) / (height [m]) 
Comorbidity profile		
Chronic obstructive pulmonary disease (COPD)	Baseline characteristic	Defined elsewhere using ICD-10 codes
Congestive heart disease	Baseline characteristic	Defined elsewhere using ICD-10 codes
Ischemic heart/coronary artery disease	Baseline characteristic	Defined elsewhere using ICD-10 codes
Diabetes	Baseline characteristic	Defined elsewhere using ICD-10 codes
Hyperlipidemia	Baseline characteristic	Defined elsewhere using ICD-10 codes
Hypertension	Baseline characteristic	Defined elsewhere using ICD-10 codes
Liver disease	Baseline characteristic	Defined elsewhere using ICD-10 codes
Renal disease	Baseline characteristic	Defined elsewhere using ICD-10 codes
Peripheral vascular disease	Baseline characteristic	Defined elsewhere using ICD-10 codes
Pregnancy	Exclusion criteria	Presence of "pregnancy"-related ICD-10 codes.

PFIZER CONFIDENTIAL

Cancer	Baseline characteristic	Defined elsewhere using ICD-10 codes
VTE	Baseline characteristic (exclusion criteria)	Defined elsewhere using ICD-10 codes
Medicines		
Anti-hypertensive drugs	Baseline characteristic	Defined elsewhere using drug codes
Anti-platelet drugs	Baseline characteristic	Defined elsewhere using drug codes
NSAIDs (chronic use*)	Baseline characteristic	Defined elsewhere using drug codes
Statins	Baseline characteristic	Defined elsewhere using drug codes
Outcomes		
Ischemic stroke (1)+(2)	Outcome	Defined elsewhere using ICD-10 codes
(1) Cardiogenic cerebral embolism	Outcome	Defined elsewhere using ICD-10 codes
(2) Cerebral infarction	Outcome	Defined elsewhere using ICD-10 codes
Hemorrhagic stroke	Outcome	Defined elsewhere using ICD-10 codes
Systemic embolism	Outcome	Defined elsewhere using ICD-10 codes
Bleeding	Outcome	
Major bleeding (Any bleeding requiring hospitalization)	Outcome	Refer to excel sheet in section 10.3
Intracranial hemorrhage	Outcome	Defined elsewhere using ICD-10 codes
Gastrointestinal tract bleeding	Outcome	Defined elsewhere using ICD-10 codes
Intraocular bleeding	Outcome	Defined elsewhere using ICD-10 codes

**\*NSAIDs chronic use**

Patients who have been prescribed NSAIDs at least a 90-day during the baseline period. For non-oral drugs, the difference between each prescription day is counted as the number of prescription days.

## 6. HANDLING OF MISSING VALUES

Patients with all required data will be excluded from the analysis.

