#### **4.1.2. Exclusion criteria**

*Patients who meet the following exclusion criteria will be excluded from this study*

1. *Patients with a diagnosis of valvular AF (standard disease code: 8846941), postoperative AF (8847772), AF associated with mechanical valve malfunction (T82.0), mechanical complication of heart valve prosthesis (T82.0), or rheumatic AF (I05-I09) during the baseline period\*\*.*
2. *Patients with a diagnosis of VTE during the baseline period*
3. *Patients who are prescribed any anticoagulant during the baseline period.*
4. *Patients who are prescribed anticoagulants other than warfarin and apixaban on the index date*
5. *Patients who were hospitalized for more than 6 months (including index date) regardless of reason for hospitalization.*

*\*\*: maximally 6 months prior to the index date. If sufficient patient information is available for the analysis, patients who cannot have a 6-month baseline period will be included in the analysis.*

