#### 7.1.2. Patient characteristic balancing

[figure not shown]
In this study, matched cohorts (warfarin cohort versus apixaban cohort) will be created. A propensity score will be calculated based on multivariable logistic regressions in order to account for confounding effects\* and to ensure that patient characteristics will be balanced between the warfarin cohort and apixaban cohort. An inverse probability of treatment weighting (IPTW) method using the calculated propensity score will be applied. To avoid sample size inflation and to ensure appropriate estimation of variances, s-IPTW (stabilized IPTW) is used here.

Balanced (after IPTW) patient clinical and demographic characteristics will be shown. Covariate balance between apixaban and warfarin cohorts after s-IPTW will be assessed in terms of the standardized differences with a threshold of 0.1. We will present the data for each variables and standardized differences in the same table side by side to ensure that two cohorts are balanced after IPTW.

\* Covariates used for the calculation of propensity score

- Gender: male or female
- Age: absolute years
- BMI: categories BMI (kg/m^2) (<18, 18 to <22, 22 to <25, 25+, missing)
- CHADS2 score: absolute score, categories (0, 1, 2, 3, 4, 5, 6)

PFIZER CONFIDENTIAL

[figure not shown]

- CHA2DS2-VASc: absolute score, categories (0, 1, 2, 3, 4, 5, 6, 7, 8, 9)
- Treatment status of the most recent stroke before the index date (outpatient treatment, inpatient treatment, missing)
- mRS (modified Rankin Scale) at time of admission due to most recent stroke (0,1,2,3,4,5, missing)
- JCS (Japan coma scale) at time of admission due to most recent stroke (I, II, III, missing)
- ADL (Activities of daily living) at time of admission due to most recent stroke (0-19, 20-39, 40-59, 60-79, 80-100, missing)
- Duration of hospitalization due to most recent stroke
- Destination after discharge from hospitalization due to most recent stroke (1 or 5 or other (2,3,4,6,7,8,9))
- Use of tPA or urokinase for treatment of most recent ischemic stroke (thrombolytic therapy)
- Type of most recent stroke stroke (TIA, ischemic stroke, cerebral bleeding, cardiogenic thromboembolism, unknown/others)
- 

*Note: in patients with a medical history of incidence multiple stroke events, only information regarding most recent stroke (i.e., stroke event closest to the index date) will be used.*

- Comorbidities
  - Hypertension
  - Heart failure in baseline

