### 7.2.3. Summary of Analyses

All analysis other than patient characteristics will be conducted as a two-sided p-value less than 0.05.

Patient characteristics will be compared using standardized difference as a cut-off value of 0.1.

Outcome/items to be examined	Analysis Cohort	Supports Protocol Objective Number	Subgroup	Statistical Method	Covariates/Strata	Missing Data

PFIZER CONFIDENTIAL

Patients characteristics	Cohorts in Step 1 and Step 2		None	unpaired t-test or Mann-Whitney U-test, categorical variables: chi-square test		No imputation
The incidence rates of stroke/SE and major bleeding per 1,000 person-years	Cohorts in Step 1 and Step 2		None	1000 person-years	Refer to section 5.4	No imputation
Interaction analysis	Cohorts in Step 1 and Step 2		None	Cox proportional hazards regression model	Warfarin/apixaban, primary/secondary	No imputation
Incidence rate of a composite of recurrent stroke (ischemic and hemorrhagic)/SE (primary effectiveness analysis)	Balanced cohorts	Effectiveness 1	None	1000 person-years	Refer to section 5.4	No imputation
Incidence of cardiogenic cerebral embolism (secondary effectiveness endpoint)	Balanced cohorts	Effectiveness 1	None	1000 person-years	Refer to section 5.4	No imputation
Incidence of cerebral infarction (secondary effectiveness endpoint)	Balanced cohorts	Effectiveness 1	None	1000 person-years	Refer to section 5.4	No imputation
Incidence rate of major bleeding (primary safety endpoint)	Balanced cohorts	Safety 1	None	1000 person-years	Refer to section 5.4	No imputation
Incidence rate of intracranial hemorrhage (secondary safety endpoint)	Balanced cohorts	Safety 1	None	1000 person-years	Refer to section 5.4	No imputation
Incidence rate of gastrointestinal bleeding (secondary safety endpoint)	Balanced cohorts	Safety 1	None	1000 person-years	Refer to section 5.4	No imputation
Incidence of rate of intraocular bleeding (secondary safety endpoint)	Balanced cohorts	Safety 1	None	1000 person-years	Refer to section 5.4	No imputation
Time course of proportion of a composite of the incidence of recurrent stroke (ischemic and hemorrhagic)/SE -free NVAF patients treated with warfarin or apixaban	Balanced cohorts	Effectiveness 2	None	Kaplan Meier curves	Refer to section 5.4	No imputation

PFIZER CONFIDENTIAL

Time course of proportion recurrent cardiogenic cerebral embolism-free NVAF patients treated with warfarin or apixaban	Balanced cohorts	Effectivess 2	None	Kaplan Meier curves	Refer to section 5.4	No imputation

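### SAP Section 6 excludes patients with complete data, and the rules on discharge destination, index date and prior anticoagulants do not fix who enters the primary analysis

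*SAP*

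**What the plan says.** **Missing data.** SAP Section 6 reads, in full, "Patients with all required data will be excluded from the analysis". The summary table in SAP 7.2.3 adds only "No imputation".

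**Propensity-score covariates.** SAP 7.1.2 gives a missing level to BMI, treatment status, mRS, JCS and ADL. Two examples are "Treatment status of the most recent stroke before the index date (outpatient treatment, inpatient treatment, missing" and "mRS (modified Rankin Scale) at time of admission due to most recent stroke (0,1,2,3,4,5, missing". The destination item is "Destination after discharge from hospitalization due to most recent stroke (1 or 5 or other (2,3,4,6,7,8,9", and its list of codes ends there. SAP 5.4 defines hospitalization days as "0 or days in hospital".

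**Index date.** Protocol 8.1.1.1 places it on the day following initiation of warfarin or apixaban. The Protocol Abstract (Data analysis) and Protocol 8.7 equate it with the initiation date. Protocol 8.1.1.7, item 1, treats the index drug as the one prescribed on that date. The readable SAP text gives no definition of its own; the SAP figures are not shown, so nothing is made of that.

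**Prior anticoagulants.** Exclusion 3 covers any time before the index date in Protocol 8.2.2, but only the baseline period in SAP 4.1.2. Exclusion 4, the same in both, looks at the index date for anticoagulants other than the two study drugs. SAP 2.1.3 assigns patients by their first oral anticoagulant after NVAF diagnosis. SAP 7.1.2 lists heparin treatment during baseline as a propensity covariate.

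**The concern.** These rules decide who is in the primary effectiveness and safety comparisons. A programmer who follows them literally builds the wrong cohort. A sensible programmer has to guess, and two could guess differently while both claim to follow the plan. The guesses are not neutral as to case mix: one possible coding of destination removes strokes and TIAs treated without admission, although no listed exclusion says so. With a retrospective database, such choices should be settled before anyone can see their effect on the hazard ratio.

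**Working it through.** **1. Section 6.** Take a patient with no recorded mRS, and suppose mRS counts as required (the SAP does not say).

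- *Literal reading:* this patient stays, and patients with everything recorded go.
- *Complete-case reading (negative restored):* this patient goes, and the missing level of mRS in 7.1.2 is never used.
- *Missing-category reading:* this patient stays, in the missing level.

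Only the third reading uses the levels that 7.1.2 sets up. Of the 13 covariates listed there before the comorbidities, 5 carry a missing level. Correcting the one word would therefore leave Section 6 and 7.1.2 at odds until the required variables are named.

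**2. Discharge destination.** Eight of those 13 covariates describe the most recent stroke. Four have a missing level (treatment status, mRS, JCS, ADL), type has an unknown/others level, thrombolysis can be coded no, and duration can be 0. That accounts for 4 + 1 + 1 + 1 = 7. Destination is the eighth, and its listed codes all refer to a discharge. If it is blank for patients who were not admitted, a standard logistic procedure omits them, and they get no score and no weight. If they are placed under other, they stay but are mixed with real discharge codes. The SAP does not choose.

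Adding *not hospitalized* and *missing* does not disturb the model. Intercept (1), treatment status (2 indicators) and destination with five levels (4 indicators) make 7 columns. Where *not hospitalized* coincides with outpatient treatment and *missing* coincides with missing treatment status, two columns are duplicates. The rank is then 5, and the fitted scores equal those from the model without the two duplicates.

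**3. Index date.** Let *d* be the day of the initiating prescription.

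| | Index = *d* + 1 (Protocol 8.1.1.1) | Index = *d* (Abstract, 8.7) |
|---|---|---|
| Protocol baseline, 180 days before index | *d* − 179 to *d* | *d* − 180 to *d* − 1 |
| Initiating prescription is before index | yes | no |
| Initiating prescription is in baseline | yes | no |
| Day checked by exclusion 4 | *d* + 1 | *d* |

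Under the first column the initiating prescription meets exclusion 3 in the Protocol (before index) and in the SAP (within baseline). Every eligible patient has such a prescription, so every one is excluded. Exclusion 4 then looks at the day after the drug was chosen.

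**4. Look-back and heparin.** SAP 2.1.3 makes the index drug the first oral anticoagulant after diagnosis, so no oral anticoagulant can lie between diagnosis and initiation. For oral agents the two versions of exclusion 3 therefore differ only for use that precedes both the NVAF diagnosis and the baseline. Heparin is a separate conflict. If it counts as an anticoagulant, SAP exclusion 3 removes every baseline user and the covariate is constant. If it does not, the exclusion must mean something narrower than it says.

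**5. Size.** The documents give no recording rates, no share treated as outpatients, no share on heparin and no share with remote anticoagulant use, so the loss cannot be computed. The only related figures are in SAP 7.2.2, and they are not in dispute. The number per group is 4(1.960 + 0.842)² / (ln HR)², divided by the sum over the two arms of 1 − exp(−2 × rate). For HR 0.6 and 1.2 %/year this is 120.3 / (0.02371 + 0.01430) = 3,166, as printed. The other cells agree within 3%.

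**The case against.** The strongest reply is that a competent reader sees a dropped negative in Section 6, and that the plan plainly means to keep outpatient-treated patients, since it gives them a treatment-status level and allows zero hospital days. The look-back difference is also narrow, and the Protocol defers detailed methods to the SAP.

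Much of this stands. The slip is very likely, the intention to keep outpatients is a fair reading, and the look-back gap is as small as step 4 shows. It does not answer the undefined required data, the missing instruction for destination, or an index date under which exclusion 3 empties the study.

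Four stronger inferences are tempting, and the documents do not support them.

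- *No outpatient-treated patient can receive a propensity score.* This is true only if destination is left blank, which the SAP does not state. A simulation that leaves it blank merely repeats the assumption.
- *Short records corrupt the NSAID adjustment.* SAP 4.1.2 does say "If sufficient patient information is available for the analysis, patients who cannot have a 6-month baseline period will be included in the analysis", and the chronic-use variable in 5.4 needs 90 days. But the propensity list in 7.1.2 uses baseline NSAID treatment with no day count.
- *The baseline lengths conflict.* The Protocol's 180 days fits within the SAP's "maximally 6 months prior to the index date", and no consequence is shown.
- *The study loses its power.* Assume HR 0.65, 15,000 patients split 1:1 and two full years of follow-up. Then 80% power needs 8,634 patients at 1.2 %/year (8,634 / 15,000 = 57.6%) and 4,034 at 2.6 %/year (26.9%). The share retained is unknown, so no shortfall follows.

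**Conclusion.** Wrong as written, and to be corrected before extraction. Section 6 reverses its own purpose and names no required variable. Destination lacks a stated level for patients who were not admitted or whose treatment status is missing, and they are lost if it is left blank. The Protocol has two index dates; under 8.1.1.1, exclusion 3 taken literally leaves nobody in either document. The look-back and the heparin rule also disagree, with a narrower effect.

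The conclusion rests on the wording alone. The documents do not show which index date, look-back or scope of anticoagulant was intended. The number of patients affected cannot be estimated.

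**What to change.** 1. Replace SAP Section 6 with a rule of this kind: patients are excluded only if data needed to define cohort, exposure or follow-up (for example age, sex or follow-up dates) are missing; missing propensity-score covariates are kept as a missing category, as in 7.1.2; exclusions are reported by arm.
2. Add *not hospitalized* and *missing* to discharge destination. Duration is numeric, so state its coding too: 0 when not hospitalized, and 0 with a missing indicator when unknown.
3. Reconcile the index date to one definition in both documents, worded so that the initiating prescription is not itself an exclusion and exclusion 4 checks the day the drug was chosen.
4. Reconcile the exclusion 3 look-back to one window in both documents, and report how many patients the other window would add or remove. Reconcile the scope of anticoagulant in the exclusions with the baseline-heparin covariate.

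The cost is a few sentences in each document, two covariate levels and a table of counts, with no new analysis. Software will set the redundant parameters to zero. Missing-category adjustment has known limits, and the SAP should list it as a limitation.

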## 7. STATISTICAL METHODOLOGY AND STATISTICAL ANALYSES

### 7.1. STATISTICAL METHODS

#### 7.1.1. Patient characteristics

Patients characteristic will be compared between two groups before and after IPTW. Means, medians, and standard deviations will be provided for continuous variables when performing descriptive analysis of continuous data. Numbers and percentages will be provided for dichotomous and polychotomous variables when performing descriptive analysis of categorical data. Bivariate comparisons of baseline characteristics and outcomes measures will be provided. Appropriate tests (unpaired t-test or Mann-Whitney U-test, categorical variables: chi-square test) will be used based on the distribution of the measure. The balance of these covariates between cohorts will be assessed using the standardized difference (cutoff: 0.1)

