8.1.1.6. Baseline period

Period of 180 days before the index date.

8.1.1.7. Follow up period:

The end of observation is the period until the first observation of the earlier of the following items.

1. discontinuation of the index OAC (warfarin or apixaban, OAC prescribed on the index date); the index treatment is considered to be discontinued if there is a continuous gap of 45 days or more between the expected refill date and the actual refill date.
2. switch to another OAC; the index treatment is regarded as switched if the index OAC was discontinued and another OAC was started within 45 days of the prescription refill date of the index OAC.
3. lack of further records in the database; if no further relevant records are added (e.g., no further refills or visits), the last date of the patient's record in the database is considered.
4. occurrence of stroke or major bleeding (endpoints).
5. elapsing of 2 years from the index date.

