8.7. Data analysis

The detailed methodology for data analysis will be described in the Statistical Analysis Plan (SAP).

As a first step, extracted patients will be divided into two cohorts, primary prevention cohort and secondary prevention cohort based on the previous diagnosis of stroke. Clinical and demographic characteristics will be compared with two cohorts at baseline and on the index date (date of the initiation of warfarin and apixaban) and incidence rates of stroke/SE and major bleeding per 1,000 person-years will be calculated during follow-up period. In addition, interaction analysis will be conducted to investigate an interaction between OAC (warfarin/apixaban) and presence or absence of the previous episode of stroke.

- As a second step, only secondary prevention cohort will be used for further analyses as follows, Crude (before IPTW) patient characteristics are compared between warfarin and apixaban cohorts using appropriate methods (continuous variables: unpaired t-test or Mann-Whitney U-test, categorical variables: chi-square test)
- A propensity score is calculated based on multinomial logistic regressions in order to account for confounding effects and to ensure that patient characteristics are balanced between the warfarin cohort and apixaban cohort. An inverse probability of treatment weighting (IPTW) method using the calculated propensity score will be applied. To avoid sample size inflation and to ensure appropriate estimation of variances, s-IPTW (stabilized IPTW) is used here.
- Balanced (after IPTW) patient clinical and demographic characteristics are shown. Covariate balance between apixaban and warfarin cohorts after s-IPTW is assessed in terms of the standardized differences with a threshold of 0.1
- Kaplan Meier curves of balanced cohorts for each endpoint are drawn.
- Incidence rates of endpoints are calculated and shown per 1000 person-years.
- Hazard ratios with 95% confidence intervals will be calculated using a Cox proportional hazards regression model that incorporate only the index OACs as independent variables.

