### 7.2.2. Power calculation

The randomized clinical trial, ARISTOTLE study, has revealed that hazard ratios of apixaban to warfarin in patients with a previous history of stroke/TIA are almost similar to those without a history of stroke/TIA ( $p$  for interaction : 0.71). The hazard ratio for Stroke/SE in the previous Japanese comparison of Apixaban and warfarin using the MDV database that will be used in this study was 0.65. Based on these two results, we can estimate that the hazard ratio in the current secondary prevention patients is also about 0.65. All statistical tests will be performed at  $p=0.05$  (two-sided) with no adjustment for multiplicity.

The following sample size calculation will be based on the significance level of 0.05 (two-sided) and power of 80%.Desired Power	Hazard Ratio	Event Rate (Control)	Required Sample Size per Group
0.8	0.6	1.2 %/year	3,166
		1.6 %/year	2,378
		2.1 %/year	1,815
		2.6 %/year	1,469
	0.7	1.2 %/year	6,083
		1.6 %/year	4,570
		2.1 %/year	3,488
		2.6 %/year	2,823
	0.8	1.2 %/year	14,683
		1.6 %/year	11,031
		2.1 %/year	8,422
		2.6 %/year	6,817

In the preliminary study, we have found that more than 15,000 secondary prevention patients with NVAF who take apixaban or warfarin.

So, probably the power may be higher than 0.8 in this study.

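### Minor: SAP 7.1.1 extends the baseline-table tests to outcome measures, against Protocol 8.7 and the SAP 7.2.3 table; a crude chi-square on events misleads if follow-up differs by drug

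*SAP*

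**What the plan says.** SAP 7.1.1 opens with "Patients characteristic will be compared between two groups before and after IPTW". It then says "Bivariate comparisons of baseline characteristics and outcomes measures will be provided. Appropriate tests (unpaired t-test or Mann-Whitney U-test, categorical variables: chi-square test", with the choice among them left to the distribution of the measure. No test in that section uses follow-up time.

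The other sections on the warfarin-apixaban comparison say something different:

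- **Protocol 8.7** confines the same tests to characteristics: "Crude (before IPTW) patient characteristics are compared between warfarin and apixaban cohorts using appropriate methods".
- **SAP 5.1 and 5.2** plan incidence rates per 1,000 person-years, Kaplan-Meier curves with a log-rank test, and Cox hazard ratios for the outcomes.
- **SAP 7.2.3** lists the t, Mann-Whitney and chi-square tests in the patient-characteristics row only. Each outcome row has person-years, Kaplan-Meier or Cox. The section also says "All analysis other than patient characteristics will be conducted as a two-sided p-value less than 0.05".
- **Protocol 8.1.1.7** ends follow-up at the earliest of discontinuation, switch, last record, stroke or major bleeding, and 2 years. On the first of these, "the index treatment is considered to be discontinued if there is a continuous gap of 45 days or more" between expected and actual refill.

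**The concern.** The outcomes are first events observed over follow-up of varying length. A chi-square on event yes/no tests whether the same proportion of each group had an event before each patient's follow-up happened to stop. The study asks about the hazard ratio. The two null hypotheses agree when follow-up is distributed alike on both drugs, and can part when it is not. Because follow-up ends when the index drug is stopped or switched, a difference in persistence between the drugs would become a difference in follow-up.

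If 7.1.1 is programmed as written, each outcome could carry a crude p-value beside the log-rank and Cox results. That p-value would respond partly to persistence rather than to risk, and it could disagree with the hazard ratio in either direction.

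**Working it through.** **1. The plan's own figure.** The sample-size table in SAP 7.2.2 can be reproduced from the log-rank (Schoenfeld) formula, events = 4(1.960 + 0.842)² / (ln HR)², divided by the sum of the two arms' 2-year event probabilities.

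- HR 0.7 at 2.1% per year: events = 246.8, rounded up to 247.
- Control probability = 1 − 0.979² = 0.0416; apixaban probability = 1 − (1 − 0.0416)^0.7 = 0.0293.
- 247 / 0.0708 = 3,487 per group, against 3,488 stated.

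All twelve cells agree within 4 patients. The table rests on a time-to-event test, so the sentence in 7.1.1 does not touch it.

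**2. Inputs for the check.**

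- From SAP 7.2.2: control rates 1.2% to 2.6% per year (2.1% used as the main case), expected HR about 0.65, more than 15,000 patients in total, two-sided 0.05.
- From Protocol 8.1.1.7: 2-year cap.
- Assumed, because the documents give no figure: an equal split (7,500 per arm), exponential event times, and exponential stopping unrelated to risk at rate c = 0.4, 0.5 or 0.6 per year. The calculation is unweighted.

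**3. Formulas.**

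- Mean follow-up, ignoring events: (1 − e^(−2c)) / c. This gives 1.38, 1.26 and 1.16 years for c = 0.4, 0.5 and 0.6.
- Probability of an observed event at hazard λ: p = λ/(λ + c) × (1 − e^(−2(λ + c))).
- Chi-square rejection: normal approximation to the difference of two proportions with n = 7,500 each.

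**4. Equal hazards, λ = 0.021, apixaban c = 0.4 (p = 0.02839).**

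| Mean follow-up, warfarin / apixaban (years) | p, warfarin | Difference / SE | Chi-square rejects |
|---|---|---|---|
| 1.38 / 1.38 | 0.02839 | 0 | 5% |
| 1.26 / 1.38 | 0.02609 | 0.00230 / 0.00266 | 14% |
| 1.16 / 1.38 | 0.02405 | 0.00434 / 0.00261 | 38% |

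For the last row, 0.00434 / 0.00261 = 1.66, and Φ(1.66 − 1.96) = 0.38. Over control rates of 1.2% to 2.6% per year the same row runs from 24% to 46%. Simulation of 1,000 datasets per scenario gave 4%, 13% and 38% for the chi-square, and 4% to 5% for the log-rank test in all three. With the follow-up reversed, so that apixaban is shorter, the rejection rates are the same but the false signal favours apixaban.

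**5. True HR 0.65, so λ = 0.01365 on apixaban.**

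| Mean follow-up, warfarin / apixaban (years) | p, warfarin / apixaban | Ratio of proportions | Chi-square power | Log-rank power |
|---|---|---|---|---|
| 1.38 / 1.38 | 0.02839 / 0.01857 | 0.65 | 98% | 98% |
| 1.16 / 1.38 | 0.02405 / 0.01857 | 0.77 | 64% | 97% |
| 1.38 / 1.16 | 0.02839 / 0.01572 | 0.55 | over 99% | 98% |

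The same hazard ratio appears diluted or exaggerated according to which drug has the shorter follow-up.

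**The case against.** The strongest reply is that this is a stray phrase. The section is headed as patient characteristics, opens with them and closes on covariate balance. The sections that specify the between-drug outcome analyses (SAP 5.1, 5.2 and 7.2.3) use follow-up time, and the analysis table lists no crude test of an outcome. SAP 7.2 ties primary testing to 5.1 and 5.2 and calls the secondary analyses exploratory. It is also open to argument whether the 0.05 rule in 7.2.3 reaches a test described under that heading. All of this stands, and it is why the point is minor. It does not remove the sentence. Protocol 8.8 sends the analysis to an outside vendor, and SAP 2.1 itself plans logistic regression for the Step 1 relative risks (a separate matter), so a programmer could take the words at face value.

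A reader might infer more than the documents support:

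- **That the tests will reject at equal hazards in this study.** Protocol 8.1.1.7 applies the same stopping rules to both drugs, and neither document gives persistence by drug. A difference is plausible but not documented. Follow-up that varies between patients but is distributed alike on both drugs leaves the chi-square at about 5%.
- **That all three tests compare crude proportions.** For an event yes/no outcome only the chi-square applies, and 7.1.1 does not define its outcome measures.
- **That a true effect would be lost.** The hazard ratio with its confidence interval remains the planned primary result, and with shorter apixaban follow-up the chi-square would overstate a benefit rather than hide it.

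**Conclusion.** The point holds as a minor internal contradiction with a possible statistical consequence. SAP 7.1.1 commits to comparing outcomes by tests that Protocol 8.7 and the SAP 7.2.3 table reserve for patient characteristics. A crude chi-square on events is a sound test of equal hazards here only if follow-up is alike on the two drugs, and the documents do not say whether it is. The distortion is none at equal mean follow-up and grows quickly: a gap of about 0.1 year roughly triples the false rejection rate (5% to 14%), and a gap of about 0.2 year takes it to about 38%. Those figures depend on the assumed equal split, exponential event and stopping times, stopping unrelated to risk, and no weighting. What is at stake is an extra p-value per outcome that may conflict with the planned analysis, and nothing in the primary estimates or the sample size.

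**What to change.** In SAP 7.1.1, delete the mention of outcome measures from the sentence on bivariate comparisons, so that the t, Mann-Whitney and chi-square tests apply to baseline characteristics only, as in Protocol 8.7. Add a sentence saying that between-drug comparisons of outcomes, before and after weighting, use only the follow-up-time methods already named in SAP 5.1, 5.2 and 7.2.3. If event counts are tabulated by drug, show them beside person-years and without a p-value.

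The cost is a small change of wording. No new data are needed, the replacement methods are already in the plan, and the only loss is a set of crude p-values.
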